3.3.2.2.2 Disease control rate

Analysis of the DCR will be based on an estimand defined according to the following attributes:

- The endpoint is disease control response as per RECIST v1.1.
- The treatment condition of interest is tusamitamab ravtansine.
- The analysis population is the all-treated population (defined in Section 2).
- Intercurrent events:
 - The study intervention discontinuation intercurrent event will be handled with the treatment policy strategy. Disease control response will be assessed based on tumor assessments regardless of study intervention discontinuation,
 - The further anticancer therapy (including further systemic anticancer therapies) intercurrent event will be handled with the "while not initiating further anticancer therapy" strategy. Disease control response will be assessed based on tumor assessments done up to the initiation of further anticancer therapy.
- The population-level summary will be the DCR, defined as the rate of participants with disease control response and two-sided 95% CIs using the Clopper-Pearson method.

In the absence of disease control response before the analysis cut-off date (taking into account the intercurrent event handling strategies), participants will be considered as non-responders, whatever the reason (including participants with non-evaluable BOR).

As a supplementary analysis, DCR as per RECIST v1.1 will also be summarized on the activity population (defined in Section 2). The same analytical approach as described above will be used.

3.3.2.2.3 Duration of response

Analysis of the DOR will be based on an estimand defined according to the following attributes:

- The endpoint is DOR.
- The treatment condition of interest is tusamitamab ravtansine.
- The analysis population is the subgroup of participants from the all-treated population (defined in Section 2) who achieved a confirmed objective response.
- Intercurrent events:
 - The study intervention discontinuation intercurrent event will be handled with the treatment policy strategy. DOR will be assessed based on tumor assessments regardless of study intervention discontinuation,
 - The further anticancer therapy (including further systemic anticancer therapies) intercurrent event will be handled with the hypothetical strategy. DOR will be assessed based on tumor assessments had a further anticancer therapy not being taken. DOR will be assessed based on tumor assessments up to the time of initiation of further anticancer therapy,
 - Two or more consecutive missing/unevaluable tumor assessments immediately before documented PD or death will be handled with the hypothetical strategy. DOR will be assessed based on tumor assessments had 2 consecutive tumor assessments not been missed immediately before documented PD or death. DOR will be assessed based on tumor assessments up to the last evaluable tumor assessment documenting no progression.
- The population-level summary will include the median DOR and associated 95% CI using Kaplan-Meier methods.

In the absence of documented disease progression or death before the analysis cut-off date (taking into account the intercurrent event handling strategies), DOR will be censored at the date of the last evaluable tumor assessment (not showing documented disease progression) performed before the analysis cut-off date. In the absence of confirmed objective response before the analysis cut-off date (taking into account the intercurrent event handling strategies), DOR will not be derived.

3.4 TERTIARY/EXPLORATORY ENDPOINT(S) ANALYSIS

Tertiary endpoints analyses are defined in Section 3.7.2 (biomarker).

Property of the Sanofi group - strictly confidential

3.4.1 Quality of life endpoints

Patient-reported outcomes (PRO) will be analyzed as tertiary endpoints in this study as described in Table 1. Four PRO scale will be used:

- The Non-Small-Cell Lung Cancer Symptom Assessment Questionnaire (NSCLC-SAQ) to evaluate time to deterioration in the overall severity of disease-related symptoms (cough, pain, dyspnea, fatigue, appetite),
- The patient global impression of severity- lung cancer symptom (PGIS-LCS),
- The patient global impression of change- lung cancer symptom (PGIC-LCS),
- The Functional Assessments of Cancer Therapy Item GP-5 (FACT-GP5) to evaluate change from baseline in overall side effect impact.

NSCLC-SAQ

The 7 items of the NSCLC-SAQ assess 5 different cardinal NSCLC related symptom concepts over a 7 days recall period: cough (1 item), pain (2 items), dyspnea (1 item), fatigue (2 items), and appetite (1 item). The measure uses a 5-point Likert-type, verbal rating scales ranging from 0: "No at All" to 4: "Very severe" for cough and pain items and from 0: "Never" to 4: "Always" for dyspnea, fatigue, and appetite items. Domain scores are calculated based on the scale developer's procedures to form a total score, where higher scores indicate higher NSCLC symptom severity (3, 4). Two pain items form a single "Pain" domain representing the highest severity of the two items, and two fatigue items form a single "Fatigue" domain by calculating their mean. The NSCLC-SAQ total score is computed as the sum of the 5 domains and ranges between 0 and 20 (5). Missing data will follow missing data/handling procedures recommended in the NSCLC-SAQ user manual. At form-level, if a respondent does not complete the NSCLC-SAQ, such as due to attrition in longitudinal studies or due to forgetting to complete an individual assessment, his or her NSCLC-SAQ score should not be computed for that time point. At item-level, if a respondent is missing any of the five domain scores, his or her NSCLC-SAQ score should not be computed. It is possible for respondents to miss one of the Pain items or one of the Fatigue items and still have a NSCLC-SAQ total score calculated. No additional imputations will be conducted for missing data.

PGIS-LCS and PGIC-LCS

The PGIS-LCS (1 item) measure severity in lung cancer symptoms at the time of assessment; while the PGIC-LCS (1 item) measure change in lung cancer symptoms over time. PGIS-LCS measure use a unidirectional verbal rating scale, with 5 options ranging from "None" to "Very severe". PGIC-LCS measure use a bi-directional response scale, with 5 options ranging from "Much better" to "Much worse" with "No change" at the midpoint.

FACT-GP5

The FACT-GP5 ("I am bothered by side effects of treatment") is a single item from the Functional Assessment of Cancer Therapy General (FACT-G) scale assesses the overall impact of treatment side effects (6). Responses are given on a 5-point Likert-type scale recalling the past 7 days. Higher scores indicate a higher degree of side effect bother (7).

Property of the Sanofi group - strictly confidential

The baseline value is defined as the last questionnaire assessment before or on the day of first IMP. PRO post-baseline assessments will consider the on-treatment period defined as the period from the first IMP administration to 30 days after the last IMP administration. No time window will be defined and visit descriptive statistics will be based on visits as reported in the database.

3.4.1.1 Completion rate

Instrument completion rate by visit will be reported for each score:

- Unadjusted completion rate by visit will be calculated as the number of participants meeting at least the minimum requirements for scoring of the instrument divided by the number of participants in the all-treated population
- Adjusted completion rate by visit will be calculated as the number of participants meeting at least the minimum requirements for scoring of the instrument among those who were expected to complete the questionnaire. To be noted that a participant is expected to complete the PRO assessment if the participant is alive and still on-treatment.

3.4.1.2 Evolution over time

Descriptive statistics will be provided for each score: NSCLC-SAQ total score as continuous data, then PGIS-LCS, PGIC-LCS and FACT-GP5 as ordinal data. Change from baseline will be presented for FACT-GP5 score. Graphical visualizations such as line graph with mean values and corresponding 95% confidence intervals might be considered.

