1.1 STUDY DESIGN

This is a single group, Phase 2, open-label, multi-center study assessing efficacy (anti-tumor activity), safety, and PK of tusamitamab ravtansine single agent in NSQ NSCLC participants with negative (ie, intensity 1+ whatever the percentage of stained tumor cells or <1% of tumor cells) or moderate (ie, intensity \geq 2+ in \geq 1% and <50% of tumor cells) CEACAM5 expression tumors and high circulating CEA (\geq 100 ng/mL) at baseline.

During the pre-screening phase, participants who were pre-screened failed in the EFC15858 Phase 3 trial with available CEACAM5 status (central assessment by immunohistochemistry, IHC) as negative or moderate expression on archival tumor tissue can be pre-screened for ACT17241 study. Participants with high circulating CEA (≥100 ng/mL) will be screened and will go through protocol screening procedures.

This study is designed to obtain preliminary efficacy, safety and PK data on tusamitamab ravtansine administered as monotherapy at 100 mg/m² Q2W to participants with NSQ NSCLC tumors with CEACAM5 moderate-negative tumor expression and high circulating CEA levels.

Approximately 285 participants will be pre-screened to achieve approximately 38 treated participants, based on an estimated pre-screening failure rate of 84% and an estimated study screening failure rate of 15%.

The cycle duration is 2 weeks. The median expected duration of study per participant is estimated as 40 weeks: up to 4 weeks for screening, a median of 24 weeks for treatment, and a median of 12 weeks for end of treatment assessments and the safety follow-up visit. Enrolled participants may receive study intervention until disease progression, unacceptable AE, initiation of a new anticancer therapy, or the participant's or Investigator's decision to stop the treatment, whichever comes first.

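### NSCLC-SAQ over time is planned as raw visit scores among those still observed, with no change from baseline, so selective loss of more symptomatic participants could look like improvement

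*SAP*

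**What the plan says.** SAP 3.4.1.2 (Evolution over time) plans descriptive statistics for each PRO score: "NSCLC-SAQ total score as continuous data, then PGIS-LCS, PGIC-LCS and FACT-GP5 as ordinal data. Change from baseline will be presented for FACT-GP5 score". The second of these sentences is limited to one instrument. A plot is optional: "Graphical visualizations such as line graph with mean values and corresponding 95% confidence intervals might be considered".

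SAP 3.4.1 decides who contributes to those summaries. "PRO post-baseline assessments will consider the on-treatment period", which runs from first dose to 30 days after last dose. Visits are not windowed: "No time window will be defined and visit descriptive statistics will be based on visits as reported in the database". For the NSCLC-SAQ, after the scoring-manual rules, "No additional imputations will be conducted for missing data". The total score runs from 0 to 20, and higher is worse.

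Three other elements bear on the point:

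- SAP 3.4.1.1 reports completion rates by visit, over all treated participants and over those expected to complete.
- SAP 3.4.1.3 analyses time to deterioration (TTD) on the NSCLC-SAQ, using a 2-point change from each participant's own baseline.
- SAP 1.1 expects "a median of 24 weeks for treatment".

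**The concern.** A sequence of visit means is naturally read as the course of symptoms in treated participants. Here the people behind the mean change from visit to visit. Treatment stops for progression, unacceptable toxicity, new therapy, or a participant or investigator decision, and at least some of these may be commoner in people who start with worse symptoms. If so, the later means come from participants who were less symptomatic from the start, and the curve drifts down with no one's score changing. There is no control arm in which the same drift could be seen. The planned summary also omits the most direct check, which is the baseline mean of the participants seen at that visit.

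**Working it through.** **Inputs from the documents.** Median treatment is 24 weeks (SAP 1.1). About 38 participants are to be treated (SAP 4: 285 × 0.16 × 0.85 = 38.76). The score range is 5 domains × 4 = 20 points (SAP 3.4.1). The meaningful change is 2 points (SAP 3.4.1.3). The plan gives no figure for the size of this effect, so there is none to reproduce.

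**Assumptions not in the documents.** Time on treatment is exponential. Baseline SD is 3 to 4 points. The hazard of stopping is multiplied by HR per SD of baseline score, with HR from 1.0 (no link) to 1.5. No participant's score changes.

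**Step 1: how many remain.** 38 × 0.5^(w/24) gives 30 at week 8, 24 at week 16, 19 at week 24, 15 at week 32 and 12 at week 40.

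**Step 2: shift in the visit mean.** With standardised baseline score z ~ N(0,1), the probability of remaining at week w is S(w|z) = exp{−(ln 2/24)·w·HR^z}. The mean of z among those remaining is E[z·S(w|z)] / E[S(w|z)]. Numerical integration gives:

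| HR per SD | Week 24 (SD units) | Week 24 (points, SD 3 to 4) | Week 32 (SD units) | Week 32 (points, SD 3 to 4) |
|---|---|---|---|---|
| 1.0 | 0 | 0 | 0 | 0 |
| 1.2 | −0.126 | −0.4 to −0.5 | −0.166 | −0.5 to −0.7 |
| 1.35 | −0.204 | −0.6 to −0.8 | −0.267 | −0.8 to −1.1 |
| 1.5 | −0.271 | −0.8 to −1.1 | −0.349 | −1.0 to −1.4 |

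The largest values are 1.1/2 = 55% and 1.4/2 = 70% of the 2-point threshold. The smallest is zero.

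**Step 3: a hand check.** Let 19 participants score 5 and 19 score 11 throughout, so the baseline mean is 8.0. If 10 low and 9 high scorers remain, the mean is (50 + 99)/19 = 7.84. If 14 and 5 remain, it is (70 + 55)/19 = 6.58. Change from baseline is 0 in both cases.

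**Step 4: does change from baseline repair it?** A separate simulation kept 50% of participants at week 24, with baseline mean 8 and SD 3 to 5 (both assumed).

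- Stopping linked only to baseline severity (HR 1.5 to 2.0 per SD): the raw mean falls by 0.8 to 1.9 points, while mean change from baseline among those remaining stays at 0.0 to 0.1.
- Stopping linked to the participant's own worsening (HR 1.5 to 2.0 per SD of change): change from baseline among those remaining is also biased, at −0.5 to −1.2 against a true value of about 0.0 to 0.1.
- Both links (HR 1.5 each) and a true mean worsening of about 1.0 point: the raw mean falls by 0.5 to 0.8, while change from baseline shows +0.3 to +0.4. The sign is right but the size is too small.

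**The case against.** The case for leaving the SAP alone has real content.

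- **The effect is conditional.** A reader might infer that the curve will show improvement, always in that direction. The documents do not support this. They give no link between stopping and baseline NSCLC-SAQ, and some stopping reasons need not track symptoms. At HR 1.0 the shift is zero. This stands.
- **The SAP matches the declared endpoints.** The endpoint table gives TTD for the NSCLC-SAQ and change from baseline only for FACT-GP5, so no declared analysis is missing. This stands, but it does not make a raw over-time summary easier to interpret.
- **Within-person change is covered elsewhere.** TTD uses each participant's own baseline, and PGIC-LCS asks directly about change. It would be wrong to say that the NSCLC-SAQ is read from raw means alone. However, TTD censors at the last on-treatment assessment and does not list death or stopping treatment as events. PGIC-LCS by visit comes from the same shrinking group. Neither corrects the visit means.
- **Attrition is shown.** Completion rates reveal how many have left, but not whether they were more symptomatic at baseline.
- **Some leavers' scores are kept.** The window extends 30 days past last dose, so some end-of-treatment scores count. They form a separate visit and do not enter later cycle means. The visit is due at 30 ± 5 days, so some will fall outside the window.
- **The shift is within the noise.** The 95% half-width of a mean is 2.101/√19 = 0.48 SD at week 24 and 2.145/√15 = 0.55 SD at week 32, against largest shifts of 0.27 and 0.35 SD. This limits the weight of the point, but a wide interval does not remove a bias.

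**Conclusion.** The point holds as a modest one. The planned NSCLC-SAQ visit means can fall through a changing mix of participants alone, by 0 to about 1.1 points at week 24 and 0 to about 1.4 at week 32. That range rests on an assumed SD of 3 to 4 points, assumed hazard ratios of 1.0 to 1.5 per SD, and exponential time on treatment with the SAP's 24-week median. None of the symptom inputs is in the documents.

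A reader might also infer that adding change from baseline makes the curve unbiased. It does not: it removes the case-mix part only, and bias remains if a participant's own worsening drives stopping. Because the analysis is tertiary, descriptive and untested, and the plot is optional, this is a worthwhile improvement that does not threaten the trial's conclusions.

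**What to change.** In SAP 3.4.1.2:

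1. Add NSCLC-SAQ total score change from baseline at each visit, with n and the baseline mean of the same participants.
2. Base any plotted NSCLC-SAQ curve on change from baseline, with n under the axis.
3. State that the values describe participants still observed, and read them beside the completion rates of SAP 3.4.1.1.

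This uses data already collected and costs a few lines of SAP text and minor programming.

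A mixed model for repeated measures is optional and not part of the required change. There are 13 post-baseline PRO visits up to Cycle 13 Day 1 (Cycle 1 Day 8 plus Day 1 of Cycles 2 to 13). An unstructured covariance would need 13 × 14/2 = 91 parameters from about 38 participants. Anyone who wants such a model should specify a reduced set of visits and a simpler covariance structure in advance.

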3.4.1.3 Time to deterioration

The time to deterioration (TTD), in disease related symptoms (cough, pain, dyspnea, fatigue, appetite) from NSCLC-SAQ, is defined as the time from baseline until the first \geq 2-point change from baseline (considered as clinically meaningful change) up to the end of treatment assessment before the analysis cutoff date (5). In case of missing score, no imputation will be done, and the assessment will be done according to the scales available.

Participants with a non-missing baseline assessment will be censored at the last on-treatment assessment before the start of further systemic anticancer therapy or before the analysis cutoff date (whichever is earlier), provided their symptoms scale had not deteriorated up to that point. Participant without baseline or post-baseline electronic patient-reported outcomes (ePROs) questionnaire or whose baseline scores do not allow further deterioration will be censored at the first IMP day.

TTD will only be analysed for the SAQ as there are no interpretation thresholds for the other measures.

TTD data will be summarized using the Kaplan-Meier method:

- Kaplan-Meier estimates of the 25th, 50th, and 75th percentiles and their associated 95% CIs will be provided. The 95% CIs will be constructed using a log-log transformation of the survival function and the method of Brookmeyer and Crowley.
- Number of participants at risks as well as the probabilities of being event-free at for example least 2, 4, 6, 8 ,10 months with 95% CIs will be estimated using the Kaplan-Meier method.
- The number of censored participants, the reasons and timing for their censoring (censored at first IMP administration, censored at last non-missing assessment before the initiation of a further systemic anti-cancer therapy, censored at last non-missing assessment before the cut-off date, censored at last non-missing on-treatment assessment). Kaplan-Meier curves will be plotted. These plots will include the number of participants at risk at key time points.

3.5 MULTIPLICITY ISSUES

No multiplicity issues are anticipated in this study.

3.6 SAFETY ANALYSES

All safety analyses will be performed on the all-treated population as defined in Section 2, unless otherwise specified, using the following common rules:

- The analysis of the safety variables will be essentially descriptive, and no testing is planned.
- Safety data in participants who do not belong to the all-treated population (eg, treated but not enrolled) will be provided.

3.6.1 Extent of exposure

The dose information will be assessed by the following:

- Number of cycles started per participant.
- Duration of exposure (in weeks) is defined by (date of last administration of the IMP + 14 days date of first administration of the IMP)/7.
- Actual dose (in mg/m²). In case of dose interruption, actual dose will be the sum of the actual doses administered before and after the dose interruption.
- Cumulative dose (in mg/m²): the cumulative dose is the sum of all actual doses of tusamitamab ravtansine, given from first to last administration
- Actual dose intensity (ADI in mg/m²/week): defined as the cumulative dose divided by the duration of tusamitamab ravtansine exposure (in weeks)

- Planned dose intensity (PDI in mg/m²/week): corresponds to the planned dose at C1D1 + planned dose at subsequent cycles multiplied by the theoretical total number of doses started 1 and divided by the theoretical cycle duration expressed in weeks (ie, 2 weeks per cycle started)
- Relative dose intensity (RDI, in %):100 × ADI ([mg/m²/week])/PDI ([mg/m²/week])

The total number of cycles started, number of cycles started by participant will be summarized as a quantitative variable and by category (number [%] of participants receiving at least 1 cycle, at least 2 cycles, etc). Duration of tusamitamab ravtansine exposure, cumulative dose, ADI and RDI will be summarized quantitatively.

The following variables will be derived to describe dose modifications and dose interruptions:

• Dose reduction: The first administration (loading dose) and second administration (first 100 mg/m² infusion) will not be counted as a dose reduction. For the third and subsequent tusamitamab ravtansine administrations, dose reduction will be determined using the dose level intervals provided in Table 6, by comparing the current dose level to the previous dose level. If the current dose level is below the dose level interval of the previous dose administration, then the current dose Table 6 level is considered reduced.

Actual dose level	Dose level interval
Starting dose (100 mg/m² Q2W)	>90 mg/m²
Dose level -1 (80 mg/m² Q2W)	>72.5 mg/m² and ≤90 mg/m²
Low dose	>0 mg/m² and ≤72.5 mg/m²

Table 6 - Tusamitamab ravtansine dose reduction criteria

- Delay: A cycle will be considered as delayed if the tusamitamab ravtansine administration date of the current cycle 14 days tusamitamab ravtansine administration date of the previous cycle is >2 days. Cycle delay is not defined for the first cycle.
- Dose interruption: A dose will be considered as interrupted if the tusamitamab ravtansine administration is stopped during an infusion regardless of whether it is restarted or not.

Dose modifications and dose interruptions will be analyzed by participant and cycle as follows:

- **Participant** (number of participants treated will be used as denominator)
 - Number (%) of participants with at least 1 dose modification
 - Number (%) of participants with at least 1 dose delayed
 - Number (%) of participants with at least 1 dose reduction
 - Number (%) of participants with a least 1 dose interruption

- Cycle (number of cycles started will be used as denominator)
 - Number (%) of cycles with at least 1 dose modification
 - Number (%) of cycles with at least 1 dose delayed
 - Number (%) of cycles with at least 1 dose reduction
 - Number (%) of cycles with at least 1 dose interruption

